#### 4.7.4.1 Orthostatic Hypotension

The number (%) of subjects experiencing orthostatic hypotension will be summarized by visit and time point. Orthostatic hypotension will be defined as a decrease in systolic blood pressure (SBP) of ≥ 20 mmHg from seated or supine to standing or in diastolic blood pressure (DBP) of ≥ 10 mmHg from seated or supine to standing. All blood pressure data, including repeat and unscheduled assessments, will be included in determining the incidence of orthostatic hypotension. If a subject has multiple results on the vital signs at a particular visit and time point, the last non-missing value at that visit/time point will be used for this summary.

A listing of subjects who experienced orthostatic hypotension will be provided.

#### 4.7.4.2 Heart Rate

The number (%) of subjects experiencing heart rate increase from pre-dose to post-dose and the number of occurrences per subject will be summarized with various threshold values (ranging from >5 bpm to >40 bpm, with threshold values increasing by 5 bpm). The median, minimum and maximum heart rate increase (in bpm) will be provided per threshold value. The number of

occurrences will be summarized using the median, minimum and maximum values. All heart rate data, including repeat and unscheduled assessments, will be included in determining the increase from pre-dose in this summary.

#### 4.7.5 Electrocardiogram

Descriptive statistics will be provided to summarize ECG parameters and changes from baseline by visit and time point. The ECG parameters include heart rate (bpm), RR interval (msec), PR interval (msec), QRS duration (msec), QT interval (msec), and QTcF (Fridericia) (msec). Results from repeat or unscheduled visits will not be included in this summary.

The number (%) of subjects experiencing heart rate increase from pre-dose to post-dose and the number of occurrences per subject will be summarized with various threshold values (ranging from >5 bpm to >40 bpm, with threshold values increasing by 5 bpm). The median, minimum and maximum heart rate increase (in bpm) will be provided per threshold value. The number of occurrences will be summarized using the median, minimum and maximum values. All ECG heart rate data, including repeat and unscheduled assessments, will be included in determining the increase from pre-dose in this summary.

Incidence of change from baseline in QTcF  $\geq 30$  msec and  $\geq 60$  msec by visit and time point will be provided. The number and percentage of subjects with post-baseline QTcF > 500 msec and change from baseline  $\geq 60$  msec in QTcF by visit and time point will be presented.

Shifts from baseline ( $\leq 450$  msec and  $>450$  msec,  $\leq 480$  msec and  $>480$  msec;  $\leq 500$  msec and  $>500$  msec) in QTcF by visit and time point will be provided.

Listings of subjects satisfying each of the above criteria will be provided.

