2.7. Month 4 (Visit 6)

- Review of medical history
- Symptom directed physical examination (see [Section 7.3](#) of main protocol)
- Blood pressure and vital signs (see [Section 7.3](#) of main protocol)
- Weight and height measurements (see [Section 7.3](#) of main protocol)
- 12-lead ECG
- Clinical assessment of new fractures
- Review subject diary
- AE and concomitant medication review
- Dispense abaloparatide, vitamin D and calcium
- Self-administration of study medication when directed by site staff after completion of pre-dose activities
- Drug accountability
- Investigator assessment of local tolerance after injection

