#### **1.2.1 Synopsis of Study Design**

This is an open-label, single-arm, multicenter study enrolling postmenopausal women with osteoporosis . The study is designed to measure the early effects of abaloparatide on tissue-based bone formation and resorption variables based on samples obtained by iliac crest bone biopsy after fluorochrome labeling. The study will consist of a Screening Period (up to 1 month), a Pretreatment Period (approximately 1 month), a Treatment Period (3 months), and a Month 4 visit one month after the last dose of study medication.

There is a sub study at one site to collect pQCT data and extend an additional 3 months of study drug administration for a total of 6 months of treatment.

The study design is presented in **Figure 1**. Full details of the protocol required assessments can be found in the Schedule of Assessments and Procedures (**Table 1**).

Figure 1: BA058-05-020 Study Design, Including Schematic of Bone Biopsy Labeling Procedure

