### **3.2 General Methods**

Continuous variables will be summarized with the following descriptive statistics: number of observations, (arithmetic) mean, standard deviation (SD), median, interquartile range (Q1 and Q3), minimum, and maximum. If the number of subjects is 1, the standard deviation will be left blank. Categorical data will be summarized with frequencies for each category and corresponding percentages.

All data listings that contain an evaluation date will contain a relative study day. Screening, pre-treatment and on-treatment study days are numbered relative to the day of the first dose of study medication which is designated as Day 1. The preceding day is Day -1, the day before that is Day -2, etc.

In listings, data will be presented with the same precision as the original data. Derived data may be rounded to 1 decimal place greater than the original data for presentation purposes.

Frequency percentages will be presented with 1 decimal.

For all summaries, the mean and median will be presented to 1 decimal place greater than the original data, standard deviation (SD) to 2 greater than the original data, and the minimum and maximum will be presented to the same number of decimal places as the original data.

The summaries will include:

- data from subjects participating in the main study (i.e., subjects with planned treatment duration of 3 months, plus 1 month after the last dose of study medication); and
- data up to Month 4 for subjects participating in the sub-study (i.e., subjects with planned treatment duration of 6 months, plus 1 month after the last dose of study medication).

All subject data (from the main study and the sub-study) will be presented in listings.

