### **3.11 Visit Windows**

Unless otherwise specified, data will not be analyzed using visit windows; instead, the nominal visit will be used.

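### The pre-dose or untimed Month 4 row of the ECG and vital-sign tables can pool main-study subjects a month off drug with sub-study subjects still dosing

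*SAP*

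**What the plan says.** SAP 3.2 defines what enters the summary tables. The first component is "data from subjects participating in the main study (i.e., subjects with planned treatment duration of 3 months, plus 1 month after the last dose"; the second is "data up to Month 4 for subjects participating in the sub-study". SAP 3.5 pools all sites, SAP 3.8 plans no subgroups, and under SAP 3.11 "data will not be analyzed using visit windows; instead, the nominal visit will be used".

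The two parts of the study are in different treatment states at that visit. SAP 1.2.1 describes the main design as ending with "a Month 4 visit one month after the last dose of study medication", and Protocol 7.2.10 places the last main-study dose at Month 3. The Addendum extends the Treatment Period to six months and moves the post-treatment visit to Month 7. Its section 2.7 lists for Month 4 (Visit 6) "Self-administration of study medication when directed by site staff after completion of pre-dose activities", with further drug dispensed. Both schedules include ECG and vital signs at Month 4.

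On output, SAP 4.7.5 states "Descriptive statistics will be provided to summarize ECG parameters and changes from baseline by visit and time point", and it tabulates QTcF categories and shifts on the same basis. SAP 4.7.4 summarises vital signs by visit, and by time point where applicable. For heart rate, SAP 4.7.4.2 adds: "The number (%) of subjects experiencing heart rate increase from pre-dose to post-dose and the number of occurrences per subject will be summarized"; SAP 4.7.5 repeats this for ECG heart rate. No section separates the two groups at Month 4, and SAP section 5 does not mention the matter.

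**The concern.** One visit label covers two treatment states. For a main-study subject, Month 4 is a follow-up visit about a month after stopping. For a continuing sub-study subject, it is an on-treatment visit in the fourth month of daily dosing. A mean, a QTcF category count or a shift count taken over both describes neither state, and it moves with the proportion of sub-study subjects present.

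This matters because Month 4 is the only scheduled off-drug ECG and vital-sign visit that reaches the tables. The sub-study's own off-drug visit, Month 7, falls after the Month 4 cut-off in SAP 3.2 and appears only in listings. A reader would naturally take the Month 4 row as post-treatment, because SAP 1.2.1 describes it that way.

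A smaller related point is that sub-study subjects have one more scheduled dosing visit through Month 4. They therefore have one more chance to contribute to the pre- to post-dose heart-rate counts.

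**Working it through.** **1. The plan's own sample size, used here only as a denominator.** SAP 3.1 gives a mean change of 9.2, SD 12.0 and 21 completers; alpha is two-sided 0.05. For a paired t-test the noncentrality is (9.2/12.0) × √21 = 3.51, and the noncentral t gives 91.6% power, which agrees with the stated minimum of 90%. Allowing for 15% drop-out, 21/0.85 = 24.7, rounded up to 25. Both figures reproduce.

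**2. Treatment state at Month 4.** Inputs are Protocol 7.2, 7.2.10, 7.2.11 and Table 1, and Addendum sections 2, 2.7, 2.8, 2.9 and Table 1. A month is 30 days (Protocol 7.2), so take Month 3 as Day 90 and Month 4 as Day 120.

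| | Main study | Sub-study, continuing |
|---|---|---|
| Last scheduled dose | Month 3 | Month 6 |
| Dose at the Month 4 visit | No | Yes, in clinic |
| ECG and vital signs at Month 4 | Yes | Yes |
| Month 4 window | ±7 days | ±4 days |
| State at Month 4 | 30 days off drug nominally | Day 116 to 124 of dosing |
| Off-drug visit | Month 4 | Month 7 |

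Within the visit windows, main-study time off drug runs from (120 − 7) − (90 + 4) = 19 days to (120 + 7) − (90 − 4) = 41 days. Sub-study subjects who stop at or before Month 3 finish the study at Month 4 (Addendum sections 2 and 3). They belong with the off-drug group.

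**3. Which rows are affected.**
- ECG descriptives, QTcF categories and QTcF shifts (SAP 4.7.5), and vital-sign descriptives (SAP 4.7.4): the pre-dose or untimed Month 4 row can hold both groups.
- One-hour post-dose Month 4 row: sub-study only, because only those subjects are dosed.
- Orthostatic hypotension (SAP 4.7.4.1): supine and standing blood pressure is required at Treatment Period visits (Protocol 7.3). A main-study standing reading at Month 4 is therefore not scheduled.
- Potentially clinically significant vital signs (SAP 4.7.4): counted over any post-baseline visit, so there is no Month 4 row.
- Laboratory data: no scheduled Month 4 collection in either part. Local tolerance at Month 4: sub-study only.

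**4. Size of the mixing.** The SAP puts the sub-study at one site and does not state its size; the Protocol plans about five sites. With k sub-study subjects still dosing among 25, the on-drug share is f = k/25:
- equal enrolment over five sites, k = 5: 5/25 = 20%;
- assumed range, k = 2 to 12: 2/25 = 8% to 12/25 = 48%.

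If the on-drug mean change is D and the off-drug mean change is 0, the pooled row shows f × D: 0.20D in the central case, 0.08D to 0.48D over the range. The documents give no value for D at a pre-dose reading.

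**5. Heart-rate counts.** Scheduled pre- and post-dose pairs through Month 4 are:
- ECG: main study 2 (Day 1, Month 3); sub-study 3.
- Vital signs: main study 3 (Day 1, Month 1, Month 3); sub-study 4.

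Assume, for illustration, a 20% chance per pair of exceeding a threshold and independence between pairs. The chance of at least one occurrence is 1 − 0.8² = 36.0%, 1 − 0.8³ = 48.8% and 1 − 0.8⁴ = 59.0% for 2, 3 and 4 pairs. SAP 4.7.4.2 and 4.7.5 report one pooled figure, so at a 20% sub-study share:
- ECG: 0.8 × 36.0 + 0.2 × 48.8 = 38.6%, against 36.0% on shared visits only (+2.6 points);
- vital signs: 0.8 × 48.8 + 0.2 × 59.0 = 50.8%, against 48.8% (+2.0 points).

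**The case against.** The best reply is that the tables are by visit and time point, and time point already does some of the separating. That stands for the one-hour post-dose row. It does not settle the other row. The SAP does not say what time-point label an undosed main-study reading receives. If the reading is filed as pre-dose, or left untimed alongside the sub-study pre-dose values, the two states mix; if it gets its own label, they separate. The plan leaves this open.

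One could also read the sub-study cut-off in SAP 3.2 as stopping short of Month 4. The parallel main-study entry runs through the month after the last dose, which is Month 4, so inclusion is the natural reading. If exclusion is meant, the SAP should say so.

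It is also fair that these are descriptive safety tables for about 25 subjects with full listings, so a determined reader could reconstruct the split. That limits the harm but does not make the tabulated row interpretable.

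Three stronger inferences are tempting, and the documents do not support them:
- **That every Month 4 table is mixed, including orthostatic hypotension.** The schedule does not show this, for the reasons in step 3 of the working.
- **That the heart-rate figures are inflated from 36% to 49%, or from 49% to 59%.** Those are contrasts between the two groups, and the SAP never makes that comparison. The pooled figure moves far less, and the extra events are genuine post-dose readings.
- **That the study loses its planned evidence on reversal.** No stated objective or endpoint concerns reversal or washout.

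**Conclusion.** The concern holds in a limited form. Followed as written, SAP 3.2 with 3.5, 3.8 and 3.11 places off-drug main-study readings and on-drug sub-study readings under one nominal Month 4 visit. Nothing keeps them apart in the pre-dose or untimed row of the by-visit ECG and vital-sign tables. This rests on the visit schedules and needs no assumption about size.

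The amount of mixing is uncertain: 20% of the row on drug under equal enrolment, 8% to 48% for an assumed 2 to 12 subjects out of 25. The resulting shift is that share of an on/off-drug difference the documents do not give, and which may be small before dosing. The effect on the pooled heart-rate counts is about 2 to 3 percentage points, given a 20% chance per pair, independence and a 20% sub-study share.

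The primary endpoint, measured at Month 3, and the power calculation are unaffected. It is worth correcting because the row as labelled can mislead and the correction is nearly free.

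**What to change.** In SAP 3.2, state that Month 4 is presented in two rows by actual treatment status, and apply this in 4.7.4 and 4.7.5, and in 4.7.4.1 wherever main-study standing readings exist at Month 4:
- *30 days after last dose*: main-study subjects, plus sub-study subjects who stopped at or before Month 3;
- *Month 4, on treatment*: sub-study subjects still dosing.

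State which time-point label an undosed Month 4 reading receives.

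For the pre- to post-dose heart-rate summaries, base the pooled counts on the scheduled dosing visits that both groups share, and show the sub-study Month 4 dose separately. The shared visits differ by measurement: Day 1 and Month 3 for ECG (no ECG is scheduled at Month 1); Day 1, Month 1 and Month 3 for vital signs.

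The cost is SAP wording and one extra row per affected table, using data already collected. The on-treatment row will rest on few subjects, which is better shown than hidden in a pooled row.

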#### 4.7.6 Clinical Fractures

The number and percentage of subjects with any post-baseline clinical fracture will be presented, together with the fracture location.

#### 4.7.7 Anti-abaloparatide Antibodies

As per Radius deviation report QE-003032 approved 27-Feb-2020, the collected immunogenicity samples will not be tested as part of this study.

## 5 CHANGES FROM THE PROTOCOL-SPECIFIED ANALYSES

The following changes from the protocol-specified analyses are included in this SAP:

1. Section 4.6.8 states that correlations between the tissue-based indices of bone formation and bone resorption with the bone turnover markers (s-PINP and s-CTX) will be evaluated using Spearman's rank correlation coefficient, instead of Pearson's correlation coefficient, due to the expected non-linear relationship between variables.
2. Section 4.7.4 provides criteria for potentially clinically significant (PCS) vital signs values with corresponding analyses.
3. Section 4.7.4.1 gives the definition for orthostatic hypotension and the analysis of this parameter.

4. Section 4.7.5 describes summaries for QTcF notable values, change from baseline values, and shifts from baseline values.
5. Section 4.7.7 states that the collected immunogenicity samples will not be tested as part of this study.

All other statements in this SAP are enhancements to the statistical considerations described in the protocol.

References

[figure not shown]

Signature Page for RAD-CLIN-001709 v1.0

Approval	 06-Mar-2020 13:03:36 GMT+0000
----------	---

Approval	 06-Mar-2020 13:37:16 GMT+0000
----------	--

Approval	 06-Mar-2020 13:50:28 GMT+0000
----------	---

Approval	 06-Mar-2020 15:01:20 GMT+0000
----------	---

[figure not shown]
Approval	 06-Mar-2020 22:18:27 GMT+0000
----------	---

Approval	 09-Mar-2020 12:03:09 GMT+0000
----------	--

Approval	 09-Mar-2020 15:07:33 GMT+0000
----------	--

Signature Page for RAD-CLIN-001709 v1.0

Signature Page for RAD-CLIN-002338 v1.0

Approval	 12-Nov-2020 15:28:40 GMT+0000
----------	---

Approval	 13-Nov-2020 08:52:08 GMT+0000
----------	---

Signature Page for RAD-CLIN-002338 v1.0
